6.3.3 Medication History

A medication history must be present in the history and recorded in the source documents:

Medication History Table

Medication Category	Complete History or Timeframe	Record in CRFs
Antiretroviral therapy	Start date of initial ART regimen, current ART regimen	Yes
Statin and other lipid-lowering therapy (prescription and non-prescription)	Complete history	Yes
Prescription drugs	Within 30 days prior to entry	Yes
Non-prescription drugs	Within 30 days prior to entry	No
Complementary and alternative medicines	Within 30 days prior to entry	No

6.3.4 Clinical Assessments

Complete Physical Exam

A complete physical examination performed at any time between screening and the entry evaluation is to include at a minimum an examination of the skin, head, mouth, and neck; auscultation of the chest; cardiac exam; abdominal exam; and examination of the lower extremities for edema. The complete physical exam will also include signs

and symptoms, diagnoses, height, weight, and vital signs (temperature, pulse, respiration rate, and blood pressure).

Targeted Physical Exam

A targeted physical examination is to be performed after screening and will be driven by any previously identified or new signs or symptoms including diagnoses that the subject has experienced since the last visit. This examination includes vital signs (temperature, pulse, respiration rate, and blood pressure).

Signs and Symptoms

At entry, record on the CRFs all signs/symptoms occurring within 30 days prior to entry.

After entry, record all Grade ≥ 1 signs/symptoms, any signs/symptoms regardless of grade that lead to a change in treatment, or that meet EAE, SAE, or ICH guidelines.

Diagnoses

At screening, record diagnoses in the medical history per section 6.3.2. At study entry and thereafter, record all new diagnoses since the last study visit identified by the ACTG criteria for clinical events and other diseases.

Concomitant Medications

Record any prescription medications taken since the last study visit, including actual or estimated start dates and stop dates in the CRF. Current non-prescription, alternative and traditional medications are recorded in the source documents and CRFs.

Study Treatment

Record all study treatment modifications, including initial doses, subject-initiated and/or protocol-mandated modifications, and inadvertent and deliberate interruptions of more than 1 day since last visit. Record any permanent discontinuation of treatment.

6.3.5 Laboratory Evaluations

Sites must refer to the DAIDS Table for Grading the Severity of Adult and Pediatric Adverse Events (DAIDS AE Grading Table), Version 2.0, November 2014, which can be found at <http://rsc.tech-res.com/safetyandpharmacovigilance/gradingtables.aspx>.

Record all protocol-required laboratory values, regardless of grade, obtained at screening and entry on the CRFs.

After entry, record all laboratory values Grade ≥ 2 . Record all lipid values (Total, HDL, and LDL cholesterol, triglycerides) regardless of grade on the CRF. All laboratory values that lead to a change in study treatment, and all serum creatinine and liver function tests (AST, ALT, alkaline phosphatase, total bilirubin) regardless of grade, must be recorded.

Hematology

Hemoglobin, hematocrit, white blood cell count (WBC), with differential, absolute neutrophil count (ANC), and platelet count.

Liver Function Tests

AST (SGOT), ALT (SGPT), alkaline phosphatase, total and direct bilirubin

Blood Chemistries

sodium, potassium, chloride, bicarbonate, random glucose, BUN, creatinine, aspartate aminotransferase (AST/SGOT), alanine aminotransferase (ALT/SGPT), alkaline phosphatase, total bilirubin, direct bilirubin, total protein, and albumin.

Fasting Lipids

Total, HDL, and LDL cholesterol, triglycerides.

If triglycerides are >400 at screening and/or high enough that LDL can't be calculated, then come back for direct LDL. Subsequent LDL should be direct in those patients.

Subjects should be instructed to fast for 8 hours prior to this test. Fasting is defined as no food or drink, except for sips of water with medications. If the subject has not been fasting, the visit must be rescheduled. Record the non-fasting status on the CRF.

Pregnancy Test

All women with reproductive potential must have a negative serum or urine beta-human chorionic gonadotropin (β -HCG) pregnancy test result at screening and within 48 hours prior to initiating protocol-specified medications and any time thereafter when pregnancy is suspected. (The urine test must have a sensitivity ≤ 50 mIU/mL).

6.3.6 Laboratory Results from Clinical Care

CD4 count and HIV-1 RNA results will be obtained from routine clinical care and available in the EMR.

6.3.7 Adherence Assessment

Adherence to all study medications will be assessed by self-report. Sites will provide adherence reinforcement, according to local standard practice throughout the study. Subjects with poor adherence will be provided counseling by the site.

6.3.8 Storage of PBMCs, Plasma and Serum for future studies

Virologic and Immunologic Studies:

40 mL of blood will be collected in EDTA tubes. Peripheral blood mononuclear cells (viable PBMCs) and plasma will be processed or stored for possible later analyses of cell-associated HIV RNA and DNA and T cell subsets, soluble and cellular markers of immune activation.

5 mL of blood will be collected in SST tubes and 3 mL in sodium citrate tubes and stored for later analyses of inflammatory biomarkers.

Pharmacology:

5 mL of blood for determination of plasma concentrations of pravastatin and rosuvastatin will be collected approximately 12 hours after dosing at weeks 2, 6, and 14. Participants will be instructed to take their study medications in the evening, about 12 hours before their clinic visit. Time of last dose and blood draw will be collected.

The samples will be processed and cryopreserved at the study repository at the Lurie Special Infectious Diseases (SID) Laboratory

7.0 CLINICAL MANAGEMENT ISSUES

7.1 Toxicity Management

Criteria for subject management, dose interruptions, modifications, and discontinuation of study treatment will be mandated only for toxicities attributable to study-provided drugs (pravastatin and rosuvastatin).

The grading system for drug toxicities is the DAIDS Table for Grading the Severity of Adult and Pediatric Adverse Events, Version 2.0, November 2014, located at <http://rsc.tech-res.com/safetyandpharmacovigilance/gradingtables.aspx>.

The lone difference between the grading system for drug toxicities used in this trial and the DAIDS Table is that our protocol has a lower threshold for grading transaminase (AST and ALT) elevations; based on the current ACC/AHA and National Lipid Association Guidelines, we consider elevation of AST or ALT ≥ 3 x ULN as grounds for holding the study drug (and a grade 3 adverse event in this protocol), and CK ≥ 10 x ULN as a grade 3 adverse event and grounds for holding the study drug.

NOTE: The HILLCLIMBER protocol chair must be notified by e-mail regarding toxicities that result in regimen interruption or discontinuation. Email: [contact]. General guidelines presented in sections 7.1.1 to 7.1.3 apply to toxicities that are not specifically discussed further below.

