7.1.3 Myalgias and Myopathy

Persons who present with significant myalgias (Grade ≥ 3 , ie, muscle pain causing inability to perform usual social and functional activities) should be evaluated with a clinical assessment that includes an evaluation of CK, serum creatinine, potassium, and urinalysis. Myopathy is defined as muscle aches, soreness, tenderness, or weakness with creatinine kinase (CK) $>10 \times$ ULN not related to exercise or other causes, including trauma. If the symptoms are associated with Grade ≥ 3 elevation in CK ($10 \times$ ULN) (see table below) that is not related to exercise or other cause, study medications should be permanently discontinued. Subjects will be followed on study, off treatment through the study termination visit with subject evaluations as per section 6.2.4.

NOTE: Mitochondrial toxicity related to nucleoside therapy and not related to study medication is a possibility, and evaluations for lactic acidosis should be considered by the subject's primary care provider.

Serum CK Toxicity Grading*

Toxicity Grade	Value
Grade 1	$3 - <6 \times$ ULN
Grade 2	$6 - <10 \times$ ULN
Grade 3	$10 - <20 \times$ ULN
Grade 4	$\geq 20 \times$ ULN

* Not related to exercise or other cause

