9.2 Endpoints

9.2.1 Primary Endpoints:

Efficacy: The primary efficacy endpoint is mean percent change in fasting LDL-c (mg/dl) from week 2 (end of run-in period) to week 14

- The mean percent change in fasting LDL-c from week 2 to week 14 will be compared for the high dose group (rosuvastatin 20mg daily uptitrated to 40mg daily) and the moderate dose group (pravastatin 40mg daily).

Safety:

- All treatment-emergent adverse events, including but not limited to:
 - Incidence of adverse event-related study drug discontinuation (following initial 2 week wash-in) or hospitalizations
 - Grade 3 or greater adverse events;
 - Study drug-related symptoms
 - CK elevation > 3x upper limit of normal;
 - AST or ALT elevation >3x upper limit of normal;

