9.6.2 Secondary Analyses

Safety and tolerability data will be summarized by treatment group.

Adverse events (signs, symptoms, and diagnoses) will be analyzed and reported using the AIDS Clinical Trials Group (ACTG) medical dictionary and standardized coding for Signs, Symptoms, and Diagnoses for Clinical and Adverse Events. Adverse events will be tabulated by treatment group and will include the number of patients for whom the event occurred, the rate of occurrence, and the severity and relationship to study drug.

Incidence of clinical and/or laboratory toxicities. The safety and tolerability measures will include:

- Time to discontinuation of any study medication due to adverse events (AEs), --
- Proportion of Grade 3 or Grade 4 clinical AEs,
- Proportion of Grade 3 or Grade 4 laboratory abnormalities,
- Summaries of all treatment-related AEs

Possible future analyses

- Measures of the HIV reservoir size
- Soluble and cellular markers of immune activation and inflammation

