10.4 Expedited Adverse Event Reporting

The adverse events (AEs) that must be reported in an expedited fashion to the IND Sponsor ([name] at Northwestern University) are all serious adverse events (SAEs) as defined by International Conference on Harmonization (ICH) guidelines regardless of relationship to the study agent(s). The protocol for reporting AEs will be as follows:

- We will report any unexpected fatal or life-threatening suspected adverse reactions to the Division of Metabolism and Endocrinology Products no later than 7 calendar days after initial receipt of the information [21 CFR 312.31(c)(2)].
- We will submit 7-day reports by rapid means of communication (facsimile or email) and will address each submission to the Regulatory Product Manager and/or to the Chief, Project Management Staff;
- We will report any (1) serious, unexpected suspected adverse reactions, (2) findings from other clinical, animal, or in-vitro studies that suggest significant human risk, and (3) a clinically important increase in the rate of a serious suspected adverse reaction to the Division of Metabolism and Endocrinology Products and to all investigators no later than 15 calendar days after determining that the information qualifies for reporting.

SAEs as defined by ICH guidelines are: deaths, life-threatening events, events that require hospitalization or prolongation of hospitalization, events that result in persistent or significant disability or incapacity, and congenital anomalies or birth defects. Important medical events as assessed by medical and scientific judgment may also be considered SAEs by the investigator and should be reported in an expedited fashion. Possible drug-induced liver injury is also considered an SAE in this study and requires expedited reporting.

The study agents that must be considered in determining relationships of AEs requiring expedited reporting to the IND Sponsor are pravastatin and rosuvastatin.

The DAIDS Table for Grading the Severity of Adult and Pediatric Adverse Events (DAIDS AE Grading Table), Version 2.0, November 2014, must be used and is available at <http://rsc.tech-res.com/safetyandpharmacovigilance/gradingtables.aspx>.

Any SAE occurring during the study and up to 28 days post the last dose of study drug must

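### The Grade 3 and higher safety endpoints name no grading table, the sections that grade AST, ALT and CK disagree, and one makes the CK grade depend on an open-label judgement of cause

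*Combined protocol and SAP*

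**What the plan says.** Section 9.2.1 lists "Grade 3 or greater adverse events" among its safety endpoints, alongside CK above 3x ULN and AST or ALT above 3x ULN. Section 9.6.2 adds "Proportion of Grade 3 or Grade 4 laboratory abnormalities". Neither says which table assigns the grade.

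Grading is described in five places:

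- **6.3.5 (laboratory evaluations):** "Sites must refer to the DAIDS Table for Grading the Severity of Adult and Pediatric Adverse Events", version 2.0, with no exception stated.
- **10.4 (expedited reporting):** the same table, "DAIDS AE Grading Table), Version 2.0, November 2014, must be used and is available at" a web address, again with no exception.
- **7.1 (toxicity management):** the same table, with one declared difference: "our protocol has a lower threshold for grading transaminase (AST and ALT) elevations". AST or ALT at or above 3x ULN is a Grade 3 adverse event for this trial. CK at or above 10x ULN is also Grade 3, with no condition on cause.
- **7.1.2:** AST or ALT strictly above 3x ULN is Grade 3, and above 6x ULN is Grade 4.
- **7.1.3:** a CK table running from Grade 1 (3 to <6x ULN) to Grade 4 (20x ULN or more), with a footnote limiting it to elevations "not related to exercise or other cause".

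On recording after entry, 6.3.5 requires laboratory values of Grade 2 or higher, any value that changes study treatment, and lipids, creatinine and liver function tests at any grade. CK is not on the any-grade list.

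**The concern.** A Grade 3+ count is only as well defined as its grading rule. Section 9 gives none, so the analyst must choose among sections that do not agree. By 7.1's own statement, some AST and ALT values are Grade 3 there and a lower grade under the table that 6.3.5 and 10.4 cite.

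CK raises a second problem. Under the 7.1.3 footnote, an elevation has a grade only when it is not put down to exercise or another cause. Allocation is open-label, so whoever makes that judgement can know whether the patient takes pravastatin or rosuvastatin. If other explanations were accepted more readily in one arm, the between-arm comparison of a main statin safety signal would be distorted.

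Section 2.0 presents the trial as a pilot for studies powered for safety, so an ambiguous count would carry into their planning.

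**Working it through.** The plan states no expected number for the graded safety endpoints. Its one sample size figure (11 per arm, 9.4) concerns LDL-c and does not bear on this point. The check is therefore a comparison of the grading text, followed by the size of one reclassification.

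**Step 1: the same value under each section.**

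| Measured value | 7.1 | 7.1.2 or 7.1.3 | 6.3.5 and 10.4 (DAIDS v2.0) |
|---|---|---|---|
| AST/ALT exactly 3.0x ULN | Grade 3 | Not Grade 3 (strict inequality) | Below Grade 3, since 7.1 calls its threshold lower |
| AST/ALT 3.5x ULN | Grade 3 | Grade 3 | Below Grade 3 if under the DAIDS cut-off, which the documents do not give |
| AST/ALT 6.5x ULN | At least Grade 3; no Grade 4 cut-off stated | Grade 4 | Cut-off not given |
| CK 10x ULN, no other cause found | Grade 3 | Grade 3 | Cut-off not given |
| CK 10x ULN, put down to exercise | Grade 3 | Outside the table | Cut-off not given |

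The AST/ALT band that changes category starts at 3x ULN. Its upper end cannot be found from the documents. The last row differs from the one above it only in attributed cause.

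**Step 2: can the counts be rebuilt from the CRF?**

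- *AST and ALT:* yes. Section 6.3.5 requires every value, so either table can be applied later.
- *CK:* not reliably. The endpoint in 9.2.1 starts above 3x ULN, while Grade 2 in 7.1.3 starts at 6x ULN. A post-entry CK above 3x and below 6x ULN meets the endpoint but, as Grade 1, need not go on the CRF unless it changes treatment.
- Whether it changes treatment is itself unclear. Section 9.5 discontinues drug at CK of 3x ULN or more at weeks 2, 6 or 10. Sections 5.1 and 7.1.1 provide for continuing with CK in that range. At week 14 treatment is complete, so no change can follow.
- A higher CK that the footnote takes out of the table has no grade in 7.1.3. If treatment is unchanged, it too could be left off the CRF.

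**Step 3: size of one reclassification.** One patient changes an arm's proportion by 100/n percentage points, where n is the number per arm. Section 9.4 gives a goal of 30 and up to 50 enrolled; the synopsis and 9.1 give 40. With 1:1 allocation:

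- 30 enrolled: 100/15 = 6.7 points
- 40 enrolled: 100/20 = 5.0 points
- 50 enrolled: 100/25 = 4.0 points

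This is a per-patient figure. The documents give no basis for estimating how many patients fall in the affected ranges.

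**The case against.** The strongest reply is that 7.1 is an announced override. It adopts DAIDS v2.0, declares one difference, and defines the lower threshold as an adverse event grade for this trial. Sections 6.3.5 and 10.4 then merely fail to repeat the exception, and in 10.4 expedited reporting is triggered by seriousness, not grade. This reading is reasonable, and it rules out describing the plan as using two incompatible systems, which a reader might infer. It does not settle the endpoint, because 7.1 sits under clinical management, 10.4 is worded as mandatory, Section 9 does not choose, and 7.1 and 7.1.2 differ at exactly 3x ULN.

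Three more objections carry weight:

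- **Assessor and bias.** The footnote names no assessor. That an unblinded investigator decides is an inference from the open-label design and from 7.1.1, where the site investigator judges relatedness. Nothing shows that causes would be accepted differently by arm. What stands is that the route is open.
- **Threshold endpoints.** AST/ALT and CK above 3x ULN are counted without grade or cause, so they partly protect the safety summary. For CK this protection depends on the values reaching the CRF. Section 6.3 does require laboratory information in source documents, so missing values could be recovered, though only by going back to source.
- **Overlap.** A reader might object that one AST value counts both as Grade 3 and as above 3x ULN. The list in 9.2.1 is a set of overlapping descriptive categories, 9.6.2 plans summaries by group, and nothing is summed, so this is harmless.

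**Conclusion.** The point holds as a gap in endpoint definition with one open route to bias. The AST/ALT Grade 3+ count depends on which section is applied, but it can be regraded from recorded values. The CK count depends on which section is applied and, under 7.1.3, on a causal judgement made in an open-label trial; CK values may also be incompletely captured on the CRF. It would be too strong to say that CK is graded only when no other cause is found, because 7.1 grades 10x ULN or more unconditionally. The defect is that the two passages conflict.

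Each affected patient shifts an arm's proportion by 4.0 to 6.7 percentage points, assuming equal arms and 30 to 50 enrolled. The total effect is unknown: it depends on DAIDS cut-offs and event rates that the documents do not give. The LDL-c endpoint is unaffected. The change is worth making before data collection, because the CK recording rule is harder to repair afterwards.

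**What to change.** 1. In 9.2.1 and 9.6.2, name one grading table for the endpoints. Either DAIDS v2.0 or the 7.1 modification would remove the ambiguity; the choice is the sponsor's.
2. State that endpoint grades are assigned to the measured AST, ALT and CK values regardless of attributed cause, and report attribution separately.
3. Add CK to the values that 6.3.5 requires at any grade.
4. Reconcile 6.3.5, 7.1, 7.1.2, 7.1.3 and 10.4, including the boundary at exactly 3x ULN and the CK footnote. The thresholds for holding or stopping drug also differ between sections and must be reconciled; which should govern is for the sponsor to decide.

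The cost is a few sentences and slightly more CRF entry for CK. The one analytic downside is that exercise-related CK rises will be counted, but by the same rule in both arms and with attribution shown beside them.

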7.1 Toxicity Management

7.1.1 General Reactions

Grade 1 or 2

Subjects who develop a Grade 1 or 2 toxicity may continue study treatment.

Grade 3

Subjects who develop a Grade 3 toxicity that is judged by the site investigator to be study drug-related should have the study drug held and the study team should be consulted. The subject should be followed closely and if the toxicity does not return to Grade ≤ 2 within 2 weeks, the study drug must be permanently discontinued with subject evaluations as per section 6.2.4.

If the study drug is resumed and the same Grade 3 toxicity recurs within 4 weeks of reintroduction, and the site investigator considers this AE related to the study drug, the drug must be permanently discontinued.

With a Grade 3 toxicity that is judged not related to the study drug by the site investigator, the study drug may be continued at the discretion of the site investigator in consultation with the study team.

Grade 4

Subjects who develop a Grade 4 toxicity will have the study drug permanently discontinued, with clinical assessments and laboratory testing as described for Grade 3 toxicity. If the investigator feels that the toxicity is clearly related to another cause and that the toxicity is not caused by the study drug, and after consultation with the study team, dosing may continue when the toxicity has resolved to Grade 2 or less.

Subjects experiencing Grade 4 toxicities should be followed closely with additional clinical assessments and laboratory testing as clinically indicated in consultation with the study team.

NOTE: Direct and indirect bilirubin elevations that reach Grade 4 elevations according to the DAIDS toxicity schema and are related to atazanavir are excluded from reporting.

7.1.2 ALT and AST elevations

ALT and AST levels will be routinely evaluated at screening, week 0, 2, 6, 10, and 14 visits. All other evaluations of ALT and AST will be performed at the discretion of the site investigator based on subject symptoms.

Grade 3

Subjects who develop *asymptomatic* $>3 \times$ ULN ALT or AST elevations (Grade 3), study drug should be held for 2 weeks and the individual should be re-evaluated 3 weeks after drug discontinuation. If at that time the ALT or AST elevation is $\leq 3 \times$ ULN and subjects remain asymptomatic, the subjects are eligible to continue on study treatment at the discretion of the site investigator. If the ALT and AST are not $\leq 3 \times$ ULN within the 2 week period, the study drug must be permanently discontinued unless the ALT and AST elevations are deemed not related to study drug upon further assessment as per the discretion of the care provider (ie, acute hepatitis A or other clear causation).

For any *symptomatic* (eg, fatigue, nausea and vomiting, right upper quadrant pain, rash or eosinophilia) ALT or AST $>3 \times$ ULN (Grade 3), study drug should be held. Subjects should be asked to return to the research site for repeat testing 2 weeks later. If repeat ALT and AST is $\leq 3 \times$ ULN and the subject is no longer symptomatic, study drug can be resumed.

Grade 4

For any ALT or AST $>6 \times$ ULN (Grade 4), the study drug should be discontinued. The subject should be brought back for repeat testing every 1 week until the ALT and AST $\leq 3 \times$ ULN. Even if ALT and AST are $\leq 3 \times$ ULN upon repeat testing for these patients, the study drug will not be restarted at that time.

NOTE: If the Grade 3 or 4 elevation is clearly related to another cause and not related to study drug (eg, acute hepatitis A infection), the subject should be brought back for repeat testing every 2 weeks for Grade 3 or every 1 week for Grade 4 until the ALT or AST $\leq 3 \times$ ULN. The local site investigators should contact the study team for approval before resuming study drug. Subjects who permanently discontinue study drug will be followed on study, off treatment through the study termination visit with subject evaluations as per section 6.2.4.

NOTE: For those subjects with ALT or AST $>3 \times$ ULN upon repeat testing, whether symptomatic or not, INR should also be performed (in addition to bilirubin and alkaline phosphatase, which will be evaluated with ALT and AST routinely) as part of the study to help determine etiology of increased LFTs. Other labs including hepatitis serologies may also be indicated and performed in the context of clinical care by PCP.

NOTE: If the subject has recurrent elevations of ALT or AST $>3 \times$ ULN but the site investigator deems the elevation not related to study drug, the site investigator must contact the study team to discuss continuation of study drug.

Abnormal ALT or AST determinations occurring in the course of clinical care should be repeated by the treating clinician. Persistently abnormal values which would trigger the toxicity guidelines above should be reported to the protocol team. If the ALT or AST abnormality is not due to another cause, eg, acute hepatitis, follow the toxicity algorithm above.

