6.2.4 Discontinuation Evaluations

Evaluations for Registered Subjects Who Do Not Start Study Treatment

Subjects who do not begin study treatment should have screening and entry forms completed and entered in the database. Beyond the entry visit, no further evaluations are required. These subjects will be replaced.

Premature Treatment Discontinuation Evaluations

Subjects who discontinue the study medications before the end of the study (Week 14) should have the Premature Treatment Discontinuation evaluations done within 7 days after stopping study drugs. They will be encouraged to continue to attend all study visits and receive study evaluations as per section 6.1 through Week 14.

Premature Study Discontinuation Evaluations

All subjects who prematurely discontinue participation in the study should have the Premature Study Discontinuation evaluations done.

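### For asymptomatic Grade 3 ALT/AST elevations, section 7.1.2 makes a permanent stop depend on recovery within 2 weeks but dates its only recheck at 3 weeks

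*Combined protocol and SAP*

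**What the plan says.** The rule for asymptomatic Grade 3 ALT/AST in section 7.1.2 has three parts.

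- Hold and recheck: "study drug should be held for 2 weeks and the individual should be re-evaluated 3 weeks after drug discontinuation".
- Eligibility: if ALT or AST is at or below 3x ULN at that recheck and there are still no symptoms, "the subjects are eligible to continue on study treatment at the discretion of the site investigator".
- Mandatory stop: if values are not at or below 3x ULN "within the 2 week period, the study drug must be permanently discontinued", unless the elevation is judged unrelated to study drug.

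Above 6x ULN a separate Grade 4 rule applies: drug is stopped and not restarted.

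Other text that bears on timing:

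- Symptomatic Grade 3, also in 7.1.2: "Subjects should be asked to return to the research site for repeat testing 2 weeks later".
- Elevations clearly due to another cause (7.1.2 NOTE): "the subject should be brought back for repeat testing every 2 weeks for Grade 3 or every 1 week for Grade 4".
- Tests outside the routine visits at weeks 0, 2, 6, 10 and 14: "All other evaluations of ALT and AST will be performed at the discretion of the site investigator based on subject symptoms".
- The general Grade 3 rule in 7.1.1: if the toxicity has not fallen to Grade 2 or lower "within 2 weeks, the study drug must be permanently discontinued with subject evaluations as per section 6.2.4".
- Section 6.2.4: subjects who stop study medication early "should have the Premature Treatment Discontinuation evaluations done within 7 days after stopping study drugs".
- Section 9.5: CK, AST or ALT of 3x ULN or more at week 2, 6 or 10 leads to discontinuation of drug at that point. It describes no hold, recheck or restart.

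**The concern.** The permanent stop and the eligibility to continue are decided by the same quantity, ALT/AST against 3x ULN, but at different times. The stop refers to day 14. Eligibility refers to day 21. The protocol dates no test in this branch that would inform the day-14 decision.

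This is an operative liver-safety rule in a population for which section 2.1 says no trial has evaluated rosuvastatin 20-40 mg. AST/ALT above 3x ULN is a listed safety endpoint (9.2.1), and required discontinuations feed the 25% interim stopping rule (9.5). Two investigators could apply 7.1.2 to the same laboratory course and reach opposite decisions, which would change who is counted as discontinued.

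**Working it through.** No published figure needs reproducing. The check is date arithmetic plus a search for any other required test.

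**Inputs.** Hold and stop limit: 2 weeks (7.1.2). Recheck: 3 weeks after drug is stopped (7.1.2). Routine on-treatment ALT/AST: weeks 2, 6, 10 and 14 (6.1, 7.1.2). Visit window: ±2 days (6.2.3). Day 0 is the day drug is stopped.

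**Step 1, the gap.** Stop limit = 2 × 7 = day 14. Recheck = 3 × 7 = day 21. Gap = 21 − 14 = 7 days. If the ±2-day window is assumed to cover the recheck, it falls on days 19 to 23 and the gap is 5 to 9 days.

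**Step 2, routine visits.** Assume drug is stopped at the visit that shows the elevation.

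| Detected | Stop due | Recheck | Next routine test | Routine test within the 2 weeks? |
|---|---|---|---|---|
| Week 2 | Week 4 | Week 5 | Week 6 | No |
| Week 6 | Week 8 | Week 9 | Week 10 | No |
| Week 10 | Week 12 | Week 13 | Week 14 | No |

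A delay of a few days before stopping moves the stop limit and the recheck equally, so the gap does not change. Week 2 is the end of run-in, and subjects with significant toxicity are not randomized, so the cases after randomization are weeks 6 and 10. At week 14 treatment is over.

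**Step 3, other provisions.**

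- Unscheduled tests are discretionary and symptom-driven, and these subjects have no symptoms.
- The 2-weekly retest covers other-cause elevations only.
- The NOTE on INR in 7.1.2 presupposes repeat testing but gives no date.
- Section 7.1.1 has a 2-week limit and close follow-up, but no dated test.
- Section 6.2.4 calls for an evaluation within 7 days of stopping drug, and the discontinuation column in 6.1 includes liver tests. Whether a temporary hold triggers it is not stated for toxicity; 7.2 links 6.2.4 to temporary discontinuation only for concomitant medication. If it does apply, a value at or below 3x ULN by day 7 meets the limit. A value still above 3x ULN leaves the day-14 question open.

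**Step 4, the conflicting case.** Above 3x ULN on day 14 and at or below 3x ULN on day 21: the stop sentence requires permanent discontinuation, and the eligibility sentence allows continuation.

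**Step 5, after the change.** With the recheck at 2 weeks, the gap is 14 − 14 = 0 days.

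**The case against.** **The rule can be followed.** A reader might infer that 7.1.2 is impossible to apply. The documents do not support that. A site can test by day 14, stop if the value is above 3x ULN, and otherwise re-evaluate on day 21. The stop sentence presupposes a value in the window, and nothing forbids obtaining one. This objection stands. What is missing is a required, dated test.

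**Restart without a result.** A 2-week hold might be read as permission to restart on day 14 with no ALT/AST value. That would mean disregarding the stop sentence, which demands recovery within the 2 weeks. If restart waits for day 21, the subject stays off drug during the gap and the cost is lost treatment time.

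**Week 3 as a check after restart.** This branch speaks of continuing treatment, whereas the symptomatic branch speaks of resuming drug. That wording could fit a restart at week 2 followed by a check at week 3. The text does not say so, and this reading still leaves no dated test for the 2-week limit. It does mean that simply moving the recheck could remove an intended safety visit, and the fix allows for that.

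**Section 9.5 may pre-empt the issue.** If discontinuation there is permanent, little of this branch remains, because asymptomatic elevations would surface mainly at routine visits. But 7.1.2 itself uses discontinuation for a hold, so 9.5 does not clearly settle the matter. It adds a second inconsistency.

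**The comparison points have limits.** The symptomatic paragraph has no 2-week stop sentence of its own. Section 7.1 reserves the general guidance for toxicities not specifically discussed further on, so whether the 7.1.1 limit binds ALT/AST is unclear. The case for 2 weeks rests mainly on the stop sentence in this branch and on the symptomatic retest date.

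**Conclusion.** The inconsistency is real and lies within one paragraph of 7.1.2. For drug-related asymptomatic ALT/AST above 3x and up to 6x ULN, the only dated recheck comes 7 days after the permanent stop falls due (5 to 9 days if the visit window applies). No test clearly required by the protocol settles the 2-week decision, and one laboratory course receives opposite instructions. Section 9.5 is not reconciled with this rule.

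The documents give no transaminase event rate, so the number affected cannot be estimated. In a trial planned at about 40 subjects it may be few or none. A reader might infer a threat to the trial's validity or to the LDL-c comparison; nothing in the documents supports that. The point should be corrected because the rule governs subject safety and the correction is cheap.

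**What to change.** 1. In 7.1.2, set the asymptomatic Grade 3 re-evaluation at 2 weeks after drug is held, as in the symptomatic branch.
2. Base both resumption and permanent discontinuation on that ALT/AST result, with no restart before it.
3. If a week-3 check after restart was intended, keep it as an additional check and say so.
4. Amend 9.5 to state either that its discontinuation for AST/ALT of 3x ULN or more is a hold managed under 7.1.2, or that it is permanent and overrides 7.1.2. This also settles who counts toward the 25% interim rule.

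Moving the stop limit to 3 weeks would also remove the conflict. It is the weaker option, because asymptomatic subjects would have no dated recheck until day 21, against day 14 for symptomatic subjects.

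The cost is a wording amendment to two sections and one recheck a week earlier, with no added visit unless the week-3 check is kept. Slower-recovering subjects would be stopped at 2 weeks, as the stop sentence already requires. For an elevation found at week 10, a subject who recovers by day 14 could restart at week 12 rather than week 13. That leaves 14 − 12 = 2 weeks on drug before the week-14 LDL-c measurement instead of 14 − 13 = 1.
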